## 4. Study Design

### 4.1 Overview

Patients presenting to the emergency department who fulfill entry criteria will be asked to participate. A screening log will be kept listing all patients considered with reasons for patients not entering the study. Any patient whose information is reviewed in consideration for the study, even if not actually approached, is to be included in the screening log. The screening log will differentiate between those who are prescreened, i.e., who are reviewed but never progress to request for consent, from those who are screened, i.e., who are approached for consent, whether or not they actually sign consent or eventually participate in the study. Qualifying patients, once they have signed consent, will be stratified by age ( $\geq$  vs <age 18) and randomized 60:40 to RHB-102 or matching placebo. All patients will undergo laboratory testing and ECG, as specified below, once they have signed consent. However, only results of the pregnancy test (for women of childbearing potential) and a finger stick blood glucose (for patients with type 2 diabetes mellitus controlled by diet or oral medications) are required prior to treatment.

Patients will be started on oral fluids  $\geq$ 30 minutes after taking study medication (second dose for patients who receive 2 doses in ED) if they have not vomited during that period. Intravenous hydration should not be administered unless the patient has vomited or is clearly unable, after a reasonable period of time has elapsed since administration of study medication, to tolerate oral fluids.

At  $4\pm0.25$  hours after initial dosing, all patients are to have a repeat 12-lead ECG. Once stable, but not less than 4 hours after initial dosing, patients may be discharged from the emergency department. If a patient leaves the ED less than 4 hours after dosing, an ECG should be obtained if at all possible, even if the patient is leaving against protocol requirements.

On discharge, patients will be given an additional 3 doses of study medication to take at 24-hour intervals if nausea persists. Patients will be contacted daily for 4 days after discharge to determine their condition. Those patients who have persistent, worsening or recurrent nausea and/or vomiting during the follow-up period may be asked to come in for follow-up assessment by study personnel.

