### 4.2 Study Drug Administration

After results of the pregnancy test and/or blood glucose (when required) are obtained and determined to be negative/within acceptable limits and the patient is randomized, the investigator or a designate will administer the first dose of study medication under observation. If the patient vomits within 15 minutes, regardless of whether pill fragments are seen, a second dose of study medication will be administered by the investigator or a designate. If a patient retches but does not actually vomit any gastric contents, no second dose will be administered. If a patient vomits again, regardless of how long after the second dose of study medication, no further study medication will be administered.

Patients vomiting  $\geq$ 30 minutes after the first dose of study medication may receive rescue antiemetics, either parenterally or orally. In addition, patients with

severe nausea  $\geq$ 30 minutes after dosing with study medication and which in the investigator's opinion requires treatment may receive rescue medication. Metoclopramide 0.3 mg/kg, maximum dose 10 mg, administered intravenously will be the default rescue medication. Oral metoclopramide or other antiemetics administered either intravenously or orally may be used at the investigator's discretion. **However, patients are not to receive ondansetron or other 5-HT3 antagonists by any route for at least 24 hours after administration of study medication either in the ED or after discharge.** The following 5-HT3 antagonists are available in the US: alosetron (Lotronex), dolasetron (Anzemet), granisetron (Sancuso and others), ondansetron (Zofran, Zuplenz and others), palonsetron (Aloxi).

Oral fluids will be administered as tolerated once a patient has not vomited for 30 minutes after dosing with study medication (second dose for those patients receiving 2 doses in the ED). Only patients who do not tolerate oral fluids after an adequate attempt at oral hydration may receive parenteral hydration. Patients are not to receive intravenous hydration until it is clear to the treating physician that the patient is clearly in need of parenteral hydration.

Patients tolerating oral fluids will be discharged once deemed stable by the attending physician but not prior to 4 hours after dosing and repeat ECG.

Patients who do not tolerate oral fluids will receive parenteral hydration.

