#### 5.2.2 Observation while in emergency department

To start immediately after administration of study medication:

- Intake and output hourly:
  - all oral and parenteral intake

- urination: number of voidings
  - vomiting: number of episodes
  - stool output: number, consistency (per scale in original protocol and per Bristol Stool Scale, Appendix I)
- Vital signs at least hourly and just prior to discharge: temperature, blood pressure, pulse, respiratory rate
- Questioning regarding adverse events: hourly and just prior to discharge
- Assessments of nausea: on signing informed consent, just prior to first dose of study medication, hourly, just prior to discharge from emergency department. A 5-point Likert scale will be used:
  - 0 No nausea
  - 1 Mild nausea
  - 2 Moderate nausea
  - 3 Severe nausea
  - 4 Nausea as bad as can be

- 12-lead ECG 4±0.25 hours after initial dose of study medication (regardless of whether dose was repeated in ED). If patient leaves ED <4 hours after dosing, an ECG should still be obtained just prior to discharge.
- Brief physical examination of pertinent systems prior to discharge

If a patient vomits ≥30 minutes after taking the first dose of study medication, requires rescue antiemetic or parenteral hydration, he or she will be considered a treatment failure. The patient will be followed according to the schedule above for a total of 4 hours from the time of first administration of study medication or until discharged home, whichever comes first. After that, for patients still in the emergency department or hospital, the patient will be followed per standard protocol, according to the patient's condition.

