6.5. Protocol Deviations

Significant protocol deviations may include, but not limited to:

- Failure to meet significant inclusion/exclusion criteria
- No evidence of adequate compliance to study medication
- Receiving excluded concomitant medication, including additional doses of study medication not administered per protocol
- Failure to obtain required efficacy data:
 - While in ER: patients who sign out AMA or who are otherwise uncooperative in providing protocol-specified efficacy or safety data, including failure to stay in ED for 4 hours following dosing for a follow-up ECG
 - After discharge: patients who fail to provide protocol-specified follow-up data, including data on drug compliance and efficacy assessments

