13. ANALYSIS OF NAUSEA

Based on ITT population and Subgroup Population 1, time to No Nausea will be displayed using Kaplan-Meier method with pvalues.

Hourly observation data in ED will be used to derive time to the first “No Nausea” as an event or censor. Time to first rescue medication and time to first IV fluid (volume >100 mL) will also be derived for censor. Time to No Nausea will be evaluated based on the following three time duration.

- Time to first No Nausea (for event or censor)
- Time to first rescue (for censor)
- Time to first IV fluid (volume > 100 mL) (for censor)

The earliest event or censor will be used for Time to No Nausea. e.g if the earliest is Time to first No Nausea event, then it will be used as an event. If the earliest is rescue or IV fluid, then the time to first rescue or first IV fluid will be used for censor.

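### Does censoring time to no nausea at rescue or IV fluid call for added counts and sensitivity analyses?

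*SAP*

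**What the plan says.** Section 13 of the Supplemental SAP covers the ITT population and Subgroup Population 1. In both, "time to No Nausea will be displayed using Kaplan-Meier method with pvalues". Three times are derived for each patient: first No Nausea on the hourly ED scores, first rescue, and first IV fluid above 100 mL. The earliest decides the outcome. No Nausea counts as an event, and "If the earliest is rescue or IV fluid, then the time to first rescue or first IV fluid will be used for censor". The section does not state what it assumes about censored patients, does not ask for numbers censored by arm or reason, and gives no second handling of rescue. It names no test. SAP 9.3 sets an age-stratified log-rank test for time-to-event endpoints, and the supplement's introduction refers readers to the main SAP for the main analyses.

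Protocol 4.2 says who may be rescued. Patients who vomit 30 minutes or more "after the first dose of study medication may receive rescue antiemetics, either parenterally or orally". So may those with severe nausea that in the investigator's "opinion requires treatment may receive rescue medication". For IV fluid: "Only patients who do not tolerate oral fluids after an adequate attempt at oral hydration may receive parenteral hydration".

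Related results are planned elsewhere. SAP 7.1 lists rescue therapy and IV hydration as separate proportion endpoints, and SAP 9.3 compares proportions by arm with the CMH test. Section 11 of the supplement tabulates reasons for failure.

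**The concern.** Kaplan-Meier and log-rank methods treat a patient censored at a given hour as having the same later chance of No Nausea as a patient still under observation then. Here the censoring event is triggered partly by the outcome, since severe nausea is itself a ground for rescue. If slower-recovering patients are removed, the curve overstates recovery in both arms. If the arms are rescued at different rates, the overstatement differs and the treatment contrast moves. A reader given only curves and p-values, without the number censored in each arm, could not judge how much weight to put on them.

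**Working it through.** **Inputs.** The documents give no figure for this endpoint, so there is none to reproduce. From the documents: hourly scores (Supplemental SAP 13), ED observation to at least 4 hours (protocol 4.1), and planned arms of 192 and 128 (protocol 7.1). Not in the documents, so assumed: recovery rates, rescue rates in the ED, and the link between them.

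**Model.** Let *p* be the proportion reaching No Nausea by 4 h had no rescue been given: 0.60 on RHB-102 and 0.50 on placebo, a true difference of 10 points. Recovery is equally likely at hours 1 to 4. Rescue risk is r1 in those who would recover and r0 = RR × r1 in those who would not, with p·r1 + (1−p)·r0 equal to the arm's rescue rate. Rescue time is uniform on 0.5–1.5 h (early) or 0.5–3.5 h (spread), with distribution function F. At hour t:

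- events d = (p/4)(1 − r1·F(t))
- at risk n = p(5−t)/4 × (1 − r1·F(t)) + (1−p)(1 − r0·F(t))
- Kaplan-Meier (KM) = 1 − Π(1 − d/n)
- cumulative incidence with rescue as a competing event (CI) = Σd

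**Worked case.** Rescue 10% on RHB-102 and 20% on placebo, RR 3, early rescue.

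- RHB-102: r1 = 0.10/(0.60 + 0.40×3) = 0.0556, r0 = 0.1667. Events 0.1458, then 0.1417 at each later hour. At risk 0.950, 0.758, 0.617, 0.475. KM = 0.628, CI = 0.571.
- Placebo: r1 = 0.20/(0.50 + 0.50×3) = 0.10, r0 = 0.30. Events 0.1188, then 0.1125. At risk 0.900, 0.688, 0.575, 0.463. KM = 0.558, CI = 0.456.

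The KM difference is 7.0 points and the CI difference 11.5. Across both rescue timings, the rule would censor about 17–18 of 192 and 23–25 of 128 patients.

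**Range** (difference in points; true value 10; rescue rates RHB-102/placebo; early and spread timing):

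| Link between rescue and recovery | Rescue | KM | CI |
|---|---|---|---|
| None | 10/20% | 10.0 | 12.5–13.5 |
| None | 20/20% | 10.0 | 8.3–8.8 |
| None | 20/10% | 10.0 | 3.9–5.6 |
| RR 3 | 10/20% | 7.0–7.7 | 11.0–11.5 |
| RR 3 | 15/30% | 4.5–5.7 | 11.6–12.2 |
| RR 3 | 20/20% | 10.5–10.6 | 8.5–9.0 |
| RR 3 | 20/10% | 13.1–13.7 | 6.4–7.4 |
| Non-recoverers only | 10/20% | 4.6–5.8 | 10.0 |
| Non-recoverers only | 15/30% | −0.3 to 1.6 | 10.0 |
| Non-recoverers only | 20/20% | 12.6–12.7 | 10.0 |
| Non-recoverers only | 20/10% | 18.1–19.2 | 10.0 |

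(Non-recoverers only: r1 = 0 and r0 = rate/(1−p), for example 0.15/0.40 = 0.375 and 0.30/0.50 = 0.60.)

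With no true difference (50% in both arms) and rescue 10/20%, KM gives 0 if rescue is unrelated to recovery and −3.2 to −2.6 at RR 3. CI gives +3.1 to +4.4 and +1.6 to +2.2.

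**A second model.** A simulation used a shared latent severity that slows recovery and raises the rescue hazard (placebo recovery hazard 0.25 per hour, hazard ratio 1.5, 400,000 patients per arm). With 10% of placebo and 5% of RHB-102 patients censored, KM gave 0.124 against a true 0.128 (moderate link) and 0.092 against 0.101 (strong link). With 40% and 20% censored and a strong link, it gave 0.051 against 0.101.

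**Would the alternatives reveal informative censoring?** At 10/20% rescue, CI exceeds KM by 2.5–3.5 points when censoring is harmless and by 3.3–4.5 at RR 3. The ranges overlap, so the gap between the two curves does not identify the problem. The other candidate, nausea scored regardless of rescue, includes the effect of the rescue drug. Its data are also limited: protocol 5.2.2 follows treatment failures on the ED schedule "for a total of 4 hours from the time of first administration of study medication or until discharged home, whichever comes first". Patients can leave sooner. Protocol 4.1 provides for this ("If a patient leaves the ED less than 4 hours after dosing, an ECG should be obtained if at all possible"), and SAP 6.5 lists it among deviations: "including failure to stay in ED for 4 hours following dosing for a follow-up ECG".

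**The case for a change.** The strongest case for a change is that doubt about independence comes from the protocol's own rescue rules, and that the bias can be large under plausible differences in rescue. The planned rescue and IV proportions are not restricted to the ED or to the time before first No Nausea. Section 11 of the supplement puts every patient who vomits into one category whether or not rescue was given, so rescued vomiters cannot be counted from it. A sentence on the assumption and a small table would cost almost nothing.

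Most of this stands as description. The assumption is unstated, it is doubtful, and no planned table in the text gives exactly these counts. It does not show that the rule is wrong. Three of the table's eleven rows (no link) leave KM exact, two more move it by less than 3 points, and the direction reverses with the arm that is rescued more. The counts need no new plan: the number censored in each arm is ordinary Kaplan-Meier output, and the split by reason falls out of the three times that section 13 already tells the analyst to derive. Overall rescue and IV rates by arm, which are planned, already tell a reader whether the arms differ in rescue. Counts alone would still not show whether rescue tracked recovery, which drives the bias.

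**Conclusion.** No change to the plan. The section leaves a reporting detail to the analyst and makes a defensible choice of what to estimate: the course of nausea had rescue or IV fluid not been given. The alternatives are different estimands, not checks on that choice. Cumulative incidence can show a difference where none exists and overlaps with the primary endpoint, which already counts rescue and IV hydration as failure.

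The size of any bias cannot be determined from the documents. Under the assumed rates, a true 10-point difference appears as 10.0 with no link, as 4.5 to 13.7 at a threefold link, and as −0.3 to 19.2 if only non-recoverers are rescued. These figures rest wholly on assumed recovery rates, rescue rates and rescue timing.

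The stakes are low. The supplement is dated June 23, 2017, after unblinding on June 3, 2017, so further analyses would be post hoc as well, and the primary analysis is untouched. The p-values should be read as exploratory, with the numbers censored in view. Confidence is moderate, because the true rescue pattern is unknown.

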14. CORRELATION BETWEEN AGE AND BASELINE SEVERITY NAUSEA

Based on the ITT population, Spearman correlation statistics will be presented between age as continuous variable and baseline nausea severity (as defined in covariate section).

15. LISTING OF REDOSED SUBJECTS DUE TO VOMITTING

Based on ITT population, a listing of patients who were redosed because they vomited within 15 minutes after the first dose will be provided. Following variables will be included:

- Subject ID
- Treatment received,

- Success/failure/LTF/unknown,
- Reason for failure (further vomiting regardless of subsequent IV fluid/rescue med, received IV fluid only, received rescue meds only, received both IV fluid and rescue med),
- Time of failure relative to FIRST dose of study med, hr:min

16. LISTING OF SUBJECTS EXCLUDED FROM SUBGROUP POPULATION 1

There were 22 subjects excluded from Subgroup Population 1. A listing of reasons being excluded from subgroup population 1 will be generated. The listing should contain Subject ID, Treatment Received, and Reason being excluded from Subgroup Population 1.
